9.3 STUDY PITFALLS AND SUGGESTED SOLUTIONS

Randomized Aim

Based on the total volume of CRT recipients at the 4 enrolling institutions and the estimated percentage of acceptance of patients to enroll in a randomized CRT-P versus CRT-D trial provided by the physician (Appendix 1) and patient (Appendix 2) surveys, it is anticipated that the actual enrollment rate will exceed the rate needed to reach the target sample size of 50 patients in Aim 1 over a 1.25-year enrollment period. The required threshold for the rate of enrollment is 0.83 patients per institution per month. If the actual enrollment rate turns out to be slower than expected, then more institutions may be added to the pilot trial. The data gathered from this pilot trial will be necessary to inform the design of a future large, non-inferiority, randomized trial of CRT-P versus CRT-D with respect to number of sites needed and duration of the enrollment phase.

The present pilot randomized trial is by necessity un-blinded, i.e. patients and physicians know whether the implanted device is a CRT-P or CRT-D. In order to better understand if there are biases in the type of patients who accept randomization, the research is to be conducted as described in Aim 2 by doing so this will provide insight into the determinants of accepting participation in the randomized trial (compare patients in Aim 1 versus Aim 2) as well as insights into the determinants of choosing a CRT-P versus CRT-D device (compare patients in Aim 2 who received CRT-P versus CRT-D).

Observational Aim

The sample size needed for Aim 2 is likely to be easily achieved as we will offer enrollment to all patients screened but not enrolled into Aim 1. We expect the patient acceptance to enroll in an observational study where no clinical decisions are imposed by the research protocol to be very high. If our estimates of enrollment turn out to be too optimistic however, we would consider adding another institution to the research protocol to mitigate this issue.

The main purpose of Aim 2 is to provide insight into which patients refuse to enroll in the large RCT and why in order to inform the design of the pivotal RCT. Since all investigators on this proposal are electrophysiologists, if the pilot proposal were to reveal that a major reason for patients' refusal to participate in a randomized study of CRT-P vs. CRT-D is because of the opinion of their referring cardiologist about the relative merits of these devices, then the pivotal RCT could be designed to include referring cardiologists as primary site investigators, which would likely mitigate this problem. This is one example for how the results of Aim 2 may inform the design of the large scale trial.

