2.3 POTENTIAL RISKS AND BENEFITS

2.3.1 KNOWN POTENTIAL RISKS

For the Aim 1 randomized trial subjects, they will be screened for appropriateness of the trial before being randomized. If there is any indication that the patient should receive a CRT-D over a CRT-P then the patient will not be considered for the trial. Once the patient is enrolled in the Aim 1 the choice to have a randomized decision will not increase any health risks to the patient. Both the CRT-P and CRT-D device implantations are part of the standard medical care for HF patients. The risks involved with the implantation of either device are comparable to those of patients not enrolled in this research study. The risks include, but are not limited to, death, stroke, heart attack, damage to the heart or lungs or veins, infections, bleeding, arrhythmias, or the need for emergent open-heart surgery. These risks are the same in patients undergoing the CRT-P or CRT-D implantation procedures but who are not enrolled in this research study. Defibrillator devices include additional risk of shocks that can occur when there is an abnormal heart rhythm detected by the device. Occasionally, the device may deliver a shock for unintended reasons (a benign heart rhythm or noise).

For the observational Aim there is no additional health risk to the patients as only the patients' health information will be collected. There is a risk that the patients personal or health information may become exposed outside of the observational trial. This risk will be minimized by using all possible safeguards to help reduce risk of exposure. This risk also applies to the Aim 1 subjects.

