4 STUDY DESIGN AND ENDPOINTS

4.1 DESCRIPTION OF THE STUDY DESIGN

The design of this pilot study is in two parts corresponding to Aims 1 and 2 (Figure 1). Aim 1 is designed as a pilot randomized, controlled trial to be conducted at 4 institutions in the United States. It will randomize older patients (≥ 75 years) who are indicated for CRT device implantation to receive a CRT-P or a CRT-D. The choice of the design of Aim 1 was intended to mimic the design of a future large, multicenter, non-inferiority trial which would provide definitive answers regarding the relative impact of CRT-P versus CRT-D on total mortality and QOL in older patients. This specific design is necessary to allow the gathering of hard data on rates of screening of patients, acceptance of enrollment, randomization, device implantation, and patient retention during follow-up. Any design variations are likely to introduce biases which would increase the chances of flawed design of the pivotal trial.

Aim 2 is a non-randomized, observational study of patients who were offered inclusion into Aim 1 but refused to participate. We speculate that a majority of those patients who refuse participation in the randomized pilot trial do so because of a strong preference for CRT-P or CRT-D. This cohort complements Aim 1 and presents an opportunity to understand the reasons why older patients may refuse enrollment into a randomized trial of CRT-P versus CRT-D and to examine the demographic and clinical determinants associated with choosing a CRT-P versus a CRT-D device. It also provides the means to measure patients' QOL and satisfaction³²⁻³⁴ with decision (CRT-P or CRT-D), at baseline and 6 months after enrollment into this observational cohort.

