5.3 OBSERVATIONAL SUBJECT ENROLLMENT

Patients identified in Aim 1 who refuse to participate will be offered to enroll in the observational cohort of Aim 2. Patients are eligible to enroll in the observational cohort at the time of implant through fourteen days' post procedure. There is a separate written, informed consent designed specifically for the prospective observational study. Sites are to collect, from all patients enrolled in Aim 2, their reason(s) why they refused enrollment in Aim 1. It is anticipated that a majority of these patients will accept participating in the observational study of Aim 2 that allows them to retain control over their decision.

The research coordinator at each site will maintain a detailed log of all patients who were offered participation in the non-randomized observational cohort, whether they signed a consent form or not. Reasons for declining participation in the research protocol of Aim 2 will be recorded. The inclusion and exclusion criteria for Aim 2 are identical to Aim 1.

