5.4 STRATEGIES FOR RECRUITMENT AND RETENTION

Patients presenting to the outpatient cardiology clinics or inpatient services of the 4 participating institutions and who are prescribed CRT device implantation or CRT-D device change-out for battery depletion will be considered for participation in this pilot randomized trial. The main investigator at each site will identify prospective patients who may require CRT device implantation. This will be achieved by screening the inpatient services and outpatient clinics of the cardiac electrophysiology services at each site. Research coordinators will verify that the prospective subjects meet all the inclusion and none of the exclusion criteria for the study. Once this information is ascertained, the investigator, research coordinator, or both will approach the patient to explain the rationale of the study and its requirements. After signing written informed consent, patients will be randomized to receive a CRT-P or a CRT-D device. Block randomization by enrolling site will be adopted. The randomization status of the patient will be communicated to the treating cardiologist. Of note, the surgical procedure for CRT-P or CRT-D implantation is similar with respect to duration and risk of the procedure, with the exception that CRT-D implantations require a larger skin incision (~1.5 inches versus 0.75 inches).

The research coordinator at each site will maintain a log of all patients who were screened for this pilot trial. The log should include reasons for why the patient did not meet either the inclusion or the exclusion criteria. Additionally, the log would also include the patient's reason for not wanting to enroll in the Aim 1 clinical trial. This log will be maintained at each individual site and redacted of identifiable information in order to send to the sponsor upon request. Use of patient initials and age will be used in place of patient's full name and date of birth.

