All patients who do not enroll in the trial, but consent to be followed, will be enrolled in a parallel observational cohort. Patients’ clinical and demographic characteristics will be examined and compared between CRT-P and CRT-D recipients using t-tests, Wilcoxon rank-sum tests, chi-squared tests, or Fisher’s Exact tests, as appropriate. Patient satisfaction among CRT-P vs. CRT-D recipients will be assessed at baseline and 6 months after enrollment using the Satisfaction with Decision Scale. The scores will be presented as mean (SD) and tested using a 2-sample t-test (or Wilcoxon test if the data are non-normally distributed). Deceased patients will be included in the analysis (assigned the lowest possible satisfaction score of 6) to avoid survival bias in the event of differential mortality in CRT-P vs. CRT-D. Cost of care will also be presented as mean (SD) and compared between the two cohorts using a 2-sample t-test (or Wilcoxon test if the data are non-normally distributed). Multivariate modeling with adjustment for selected patient factors will be considered if there are differences in CRT-P vs. CRT-D patients on key demographics, but the power to test this difference while accounting for multiple confounders may be limited.

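### Sections 9.1 and 9.3 define the Aim 2 cohort more broadly than the précis and sections 4.1 and 5.3, so eligible patients never offered randomization could be counted as refusers

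*Combined protocol and SAP*

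**What the plan says.** The narrow definition appears in the précis and in two design sections. Section 4.1: "Aim 2 is a non-randomized, observational study of patients who were offered inclusion into Aim 1 but refused to participate". Section 5.3: "Patients identified in Aim 1 who refuse to participate will be offered to enroll in the observational cohort of Aim 2". Section 5.3 also sets two conditions that bear on the point: "The inclusion and exclusion criteria for Aim 2 are identical to Aim 1", and "Sites are to collect, from all patients enrolled in Aim 2, their reason(s) why they refused enrollment in Aim 1".

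The broad definition appears in the statistical section. Section 9.1 (Observational Aim): "All patients who do not enroll in the trial, but consent to be followed, will be enrolled in a parallel observational cohort". Section 9.3 (Observational Aim): "we will offer enrollment to all patients screened but not enrolled into Aim 1". Neither sentence mentions an offer or a refusal.

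Section 4.2.2 makes predictors of refusing participation the secondary endpoint. Section 9.3 says the determinants of accepting the trial will come from comparing Aim 1 with Aim 2, and the determinants of device choice from comparing CRT-P with CRT-D recipients within Aim 2. It gives the main purpose of Aim 2 as learning which patients refuse, and why, to inform the pivotal trial.

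**The concern.** In the refusal comparison, belonging to Aim 2 is the outcome. A patient in Aim 2 is treated as having refused and a patient in Aim 1 as having accepted. That holds only if everyone in Aim 2 was offered randomization and declined. An entry rule that admits anyone else misclassifies the outcome.

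Two kinds of patient can meet every criterion in sections 5.1 and 5.2 without being offered Aim 1. Section 2.3.1 describes the first: "If there is any indication that the patient should receive a CRT-D over a CRT-P then the patient will not be considered for the trial". The second follows from the entry window in section 5.3, which runs from implant through fourteen days after the procedure. A patient missed before implant can no longer be randomized but can still be approached for Aim 2.

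If patients of the first kind enter, clinical features that lead physicians towards a CRT-D would look like predictors of patient refusal. For the second kind the direction cannot be predicted. In both cases the pivotal trial would be informed partly by people who never faced the decision being studied.

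**Working it through.** **1. The plan's own figures.** Inputs from section 9.2: 50 to be randomized, 40% of those offered accept, 80% of decliners join Aim 2.

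- Approached: 50 / 0.40 = 125.
- Decliners: 125 − 50 = 75.
- Aim 2 cohort: 75 × 0.80 = 60, as stated.
- Power with 30 per group and a 0.75 SD difference: 81.5% by t-test, against 80% stated. This assumes two-sided alpha 0.05, which the documents do not give.

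The figures reproduce, and the 60 contains decliners only.

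**2. Who enters under each wording.** The section 5.3 criteria are applied in both columns.

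| Patient | Précis, 4.1, 5.3 | 9.1, 9.3 |
|---|---|---|
| Eligible, offered Aim 1, declined | may enter | may enter |
| Fails 5.1 or 5.2 | barred | barred |
| Eligible, not considered under 2.3.1 | no | may enter |
| Eligible, missed before implant, approached within fourteen days | no | may enter |

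The definitions differ only in the last two rows.

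**3. Effect on the refusal comparison.** Let m be the share of Aim 2 never offered Aim 1, p the prevalence of some characteristic among true decliners, and q its prevalence among the never-offered. Aim 2 then shows (1 − m)p + mq, and the error is m(q − p). The documents give none of these values. As an assumption, take m = 10%, 20% and 30%:

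- Patients: 0.10 × 60 = 6, 0.20 × 60 = 12, 0.30 × 60 = 18.
- If q − p = 0.5: error of 5, 10 and 15 percentage points.
- At the limit q − p = 1: 10, 20 and 30 points.

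**4. How large the pool might be.** If a share e of screened patients is offered Aim 1, reaching 125 offers requires 125/e screened. The never-offered share of those screened but not enrolled is (125/e − 125) / (125/e − 50).

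- e = 100%: 0%.
- e = 90%: 13.9 / 88.9 = 16%.
- e = 75%: 41.7 / 116.7 = 36%.

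These are upper bounds for this pool, because patients who fail the criteria must still be removed. The share within Aim 2 also depends on how often each group consents. The documents do not give e.

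**5. Effect on the device-choice comparison (secondary).** Take the worst case in which every never-offered patient receives a CRT-D, and let b be the CRT-D share among decliners. The CRT-D share of Aim 2 is b(1 − m) + m, and the never-offered share of the CRT-D group is m / [b(1 − m) + m].

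| m | b = 50% (section 9.2): CRT-D share; never offered | b = 80% (section 2.2 reports more than 80%): CRT-D share; never offered |
|---|---|---|
| 10% | 55%; 18% | 82%; 12% |
| 20% | 60%; 33% | 84%; 24% |
| 30% | 65%; 46% | 86%; 35% |

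**The case against.** The strongest defence is that section 5.3 is the operative entry rule and is clear. It names refusers and requires a refusal reason from every Aim 2 patient, which someone never offered Aim 1 could not give. Section 9.1 introduces an analysis and section 9.3 is feasibility commentary, so neither is an enrollment procedure. Section 9.2 also moves from patients offered to patients screened as if they were the same, which suggests that section 9.3 means decliners. This stands as evidence of intent. It does not remove the conflict: section 5.4 uses screening in the wider sense ("The log should include reasons for why the patient did not meet either the inclusion or the exclusion criteria"), and section 9.1 states no restriction to refusers.

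The group created by section 2.3.1 may also be small. Exclusion 3 in section 5.2 already removes prior cardiac arrest and documented sustained ventricular arrhythmia, and section 2.1 says guidelines do not separate CRT-P from CRT-D indications. Section 2.3.1 could be read as a summary of exclusion 3. But its wording covers any indication, which is wider than exclusion 3, and the post-implant route does not depend on it.

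Finally, non-refusers might be detected from a blank refusal reason or from the screening log. That is partly true. However, Tables 1 and 2 list no offered or declined status, the log stays at the site and goes to the sponsor only on request, and the plan does not say how the analysis would treat such patients.

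A reader might also infer that Aim 2 patients who were not offered randomization made no device choice. The documents do not support this. Section 6 asks every Aim 2 patient about the device decision and the reasons for it, and section 9.3 says the protocol imposes no clinical decisions. A clinical indication appearing as a determinant of device choice is partly what that comparison is meant to find.

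**Conclusion.** The conflict is real but narrow. Sections 9.1 and 9.3 would admit eligible patients who were never offered Aim 1; the précis and sections 4.1 and 5.3 would not. If sites followed the broad wording, the predictors of refusal would be biased by m(q − p). The effect on the CRT-P versus CRT-D comparison is secondary.

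The size cannot be stated, because the documents do not give the share never offered. Every percentage for m, e and q − p above is an assumption, and the device-choice figures also assume that all never-offered patients receive a CRT-D.

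Two stronger readings should be resisted. One is that every screened patient not enrolled, including those who fail eligibility, can enter Aim 2; the identical criteria in section 5.3 rule that out. The other is that the Aim 2 sample size is wrong; section 9.2 builds the 60 from decliners and the arithmetic holds. Nor do the documents show that such patients will enter, only that two sections would allow it.

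**What to change.** - In sections 9.1 and 9.3 (Observational Aim), replace the broad wording with: *eligible patients who were offered Aim 1 and declined randomization*.
- Add a field to the Aim 2 enrollment form recording whether Aim 1 was offered and whether it was declined.
- In section 9.1, restrict the refusal analysis (Aim 1 versus Aim 2) to documented decliners, and report any other followed patients separately.

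The cost is two sentences, one form field, one line of analysis plan and possibly a few fewer Aim 2 patients. The target of 60 is unchanged, because it is already 80% of 75 decliners.

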10 SOURCE DOCUMENTS AND ACCESS TO SOURCE DATA/DOCUMENTS

The individual study sites will maintain a patient binder to include all source documents that correlate with the information that is obtained with this trial. The sponsor has the right to request redacted source documents to aid in verification of information provided for the sole purpose of the trial. With each adverse event that is reported, the sites will submit all source documents pertaining to that event. These records will also be redacted of any patient identifiable information and marked with the corresponding patient identification number and correlating case report form. Each site is responsible for maintaining a patient log that indicates the patient that corresponds with their study identification number.

11 QUALITY ASSURANCE AND QUALITY CONTROL

QC procedures will be implemented beginning with the data entry system and data QC checks will be run on the database for reports to be generated. Any missing data or data anomalies will be communicated to the site(s) for clarification/resolution. Each site is responsible for conducting the clinical trial and that the data is generated, documented (recorded), and reported in compliance with the protocol, GCP, and the applicable regulatory requirements. The investigational sites will provide access to all trial related information, source data/documents, and reports for the purpose of monitoring and auditing by the sponsor.

12 ETHICS/PROTECTION OF HUMAN SUBJECTS

12.1 ETHICAL STANDARD

The investigator at each site will ensure that this study is conducted in full conformity with Regulations for the Protection of Human Subjects of Research. All personal planning to be involved must ensure that the trial is performed and the data are generated, documented (recorded), and reported in compliance with GCP and the applicable regulatory requirement(s).

12.2 INSTITUTIONAL REVIEW BOARD

The protocol, informed consent form(s), and all participant materials will be submitted to the IRB for review and approval. Approval of both the protocol and the consent form must be obtained before any participant is enrolled. Any amendment to the protocol will require review and approval by the IRB before the changes are implemented to the study. All changes to the consent form will also need IRB approval; a determination will be made regarding whether previously consented participants need to be re-consented. Any changes to the consent by the individual sites will first be required to obtain approval from the sponsor prior to submitting changes to the IRB.

12.3 INFORMED CONSENT PROCESS

Informed consent is a process that is initiated prior to the individual's agreeing to participate in the study and continues throughout the individual's study participation. Participants and their families should be informed of risks and possible benefits of participation. Consent forms will be IRB-approved and the participant will be asked to read and review the document. The investigator will explain the research study to the participant and answer any questions that may arise. All participants will receive a verbal explanation in terms suited to their comprehension of the purposes, procedures, and potential risks of the study and of their rights as research participants. Participants will have the opportunity to carefully review the written consent form and ask questions prior to signing.

The participants should have the opportunity to discuss the study with their family members or think about it prior to agreeing to participate. The participant will sign the informed consent document prior to any procedures being done specifically for the study. The participants may withdraw consent at any time throughout the course of the trial. A copy of the informed consent document will be given to the participants for their records. The rights and welfare of the participants will be protected by emphasizing to them that the quality of their medical care will not be adversely affected if they decline to participate in this study. Additionally, each informed consent process will be documented and maintained with the original copy of the consent at each study site according their institutional SOP.

12.4 PARTICIPANT AND DATA CONFIDENTIALITY

Participant confidentiality is strictly held in trust by the participating investigators, their staff, and the sponsor. This confidentiality is extended to cover clinical information relating to participants. Therefore, the study protocol, documentation, data, and all other information generated will be held in strict confidence. No information concerning the study or the data will be released to any unauthorized third party without prior written approval of the sponsor. The study participant's contact information will be securely stored at each clinical site for internal use during the study. At the end of the study, all records will continue to be kept in a secure location for as long a period as dictated by local IRB and Institutional regulations.

Study participant research data, which is for purposes of statistical analysis and scientific reporting, will be transmitted to and stored at UPMC. This will not include the participant's contact or identifying information. Rather, individual participants and their research data will be identified by a unique study identification number. The study data entry and study management systems used by clinical sites and by UPMC research staff will be secured and password protected. At the end of the study, all study databases will be de-identified and archived at the UPMC.

